7.9.1.1 Hypothesis

The primary effectiveness hypothesis is to test if the surgical success rate is above the performance goal. A performance goal of 85% (100% - conversion rate) is pre-defined to evaluate the surgical success rate. Let P be the surgical success rate in this study. The statistical hypothesis is as follows:

$$H_0: P \leq 85\% \text{ vs. } H_a: P > 85\%$$

7.9.1.2 Endpoint Definition and Derivation

Sites are asked if the procedure was completed according to the surgical plan (Yes/No). If the answer was “No”, the site reported what was not done per the surgical plan; if the site specifies “Converted”, then the surgery is identified as a conversion. Surgical success is defined as a surgery that has not involved a conversion.

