### 5.2 Endpoints

#### 5.2.1 Primary Endpoints

The primary effectiveness endpoint is the surgical success rate defined as the procedure not going into conversion. Conversion is defined as the switch from the robotic-assisted approach using the Hugo™ RAS system to laparoscopic, open surgery, or use of an alternative robotic-assisted system.

Procedural steps that are usually performed without robotic assistance per standard of care, including but not limited to mesh insertion, suture needle removal, or tacking, are not considered a conversion and will not contribute to the primary effectiveness endpoint.

The primary safety endpoint is the overall rate of subjects with one or more study procedure- and/or device-related surgical-site events (SSEs), from the first incision through 30 days post-procedure. SSE is defined as the following complications:

*Medtronic Business Restricted*

- Surgical-site occurrence (SSO):
  - Bleeding, Hemorrhage: Requiring transfusion
  - Bowel Injury
  - Bowel Obstruction
    - Note: Functional obstruction associated with general anesthesia and/or pain killer drugs (opioids) is excluded for this endpoint
  - Cellulitis
  - Epigastric Vessel Injury
  - Symptomatic Hematoma: Requiring procedural intervention
  - Symptomatic Seroma: Requiring procedural intervention
  - Symptomatic Edema: Requiring procedural intervention
    - Note: Procedural intervention is defined as percutaneous drainage, wound opening or debridement, suture excision, or mesh removal (partial or total)
- Surgical-site infection (SSI): Infection occurring where the surgery took place, including superficial, deep, and organ space infections (standardized definition developed by the CDC)

The relatedness of the SSEs being classified as “procedure- and/or device-related” may include three scenarios: (1) only procedure-related SSEs, (2) only device-related SSEs, and (3) SSEs that are both procedure- and device-related. In this study procedure-relatedness refers to an AE that occurs due to the hernia repair procedure with the Hugo™ RAS system, and device-relatedness refers to an AE that results from the presence or performance (intended or otherwise) of the Hugo™ RAS system.

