## 9.2 Subject Enrollment

A subject is considered enrolled in the study when the informed consent form is signed and dated. As soon as the surgical procedure has begun with the Medtronic Hugo™ RAS system, the subject must be followed regardless of whether the subject completed the surgical procedure with the Medtronic Hugo™ RAS system. Subject enrollment will be consecutive at the institution according to required procedure types and eligibility criteria. See **Section 14** for additional details.

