**Table 7. Data Collection and Study Procedure Requirements at Subject Visits**

Procedure/Assessment	Screening (Day -30 to 0) Visit 1	Surgical Procedure (Day 0) Visit 2	Hospital Discharge Visit 2.1	Follow-Up (30±7 Days) Visit 3	Follow- Up (3- Months ±14 Days) Visit 4	Follow-Up (Years 1-2 ±30 Days) Visit 5-6 (Phone)
	May be Combined					
Informed Consent Form 	X					
Eligibility Criteria	X	X				
Demographic Data	X					
Medical/Surgical History	X					
Concomitant Medication(s)	X	X	X	X	X	X
Robot Setup Time		X				
Total Operative Time (skin to skin)		X				
Surgeon Console Time		X				
Instruments Used		X				
Estimated Blood Loss		X				
Transfusion 		X	X	X	X	
Conversion to a laparoscopic, open surgery, or use of an alternative robotic-assisted system		X				
Robot Take Down Time		X				
Mortality			X	X	X	X
Length of Hospital Stay			X			
Reoperation			X	X	X	X
Pain Medication 			X	X	X	X
Adverse Events and Device Deficiencies 	X	X	X	X	X	X

*Medtronic Business Restricted*

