4.1.1 Primary Objective #1 (Effectiveness) Endpoint

The primary effectiveness endpoint is the surgical success rate defined as the procedure not going into conversion. Conversion is defined as the switch from the robotic-assisted approach using the Hugo™ RAS system to laparoscopic, open surgery, or use of an alternative robotic-assisted system. Procedural steps that are usually performed without robotic assistance per standard of care, including but not limited to mesh insertion, suture needle removal, or tacking, are not considered a conversion and will not contribute to the primary effectiveness endpoint.

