7.1.3 Analysis Sets

The following populations will be considered for the analysis of data for this study. All enrolled subjects will be included in a subject disposition table indicating reasons for exclusion from each analysis set.

Enrolled Analysis Set

All subjects who signed informed consent.

Full Analysis Set

The full analysis set (FAS) is defined as all enrolled subjects in whom the Hugo™ RAS procedure is begun, defined as the first skin incision. If a subject is consented, but the first incision does not occur (e.g., if the subject becomes ineligible during the timeframe between consent and the procedure day), the subject will not be considered part of the FAS. The FAS will be the primary analysis set for the evaluation of the primary, secondary, and ancillary endpoints. In the case of missing data with no imputation, some subjects may be excluded from an objective analysis using the FAS analysis set. Consider imputation plans defined in section 7.4.

Per Protocol Analysis Set

The per protocol analysis set (PPAS) is a subset of the FAS including only those subjects without any major protocol deviations. Major deviation reasons include “Enrolled subject did not meet enrollment criteria” and “Unauthorized use of investigational device.” Reasons for exclusion of subjects from PPAS will be documented in the CSR.

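### A procedure stopped after incision without a switch to another method is scored as a surgical success in the primary effectiveness test

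*SAP*

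**What the plan says.** Protocol 5.2.1 sets the endpoint: "The primary effectiveness endpoint is the surgical success rate defined as the procedure not going into conversion". SAP 4.1.1 defines the failure event: "Conversion is defined as the switch from the robotic-assisted approach using the Hugo™ RAS system to laparoscopic, open surgery, or use of an alternative robotic-assisted".

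SAP 7.9.1.2 turns this into a derivation. "Sites are asked if the procedure was completed according to the surgical plan (Yes/No"). If the answer is No and the site specifies Converted, "then the surgery is identified as a conversion". The section closes with the rule "Surgical success is defined as a surgery that has not involved a conversion". It gives no rule for any other reason behind a No.

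The primary analysis set, per SAP 7.1.3, is "all enrolled subjects in whom the Hugo™ RAS procedure is begun, defined as the first skin incision". Protocol 9.2 foresees procedures not finished with the device, since subjects are followed "regardless of whether the subject completed the surgical procedure with the Medtronic Hugo™ RAS system". Table 7 of the protocol lists this data element at the surgical visit: "Conversion to a laparoscopic, open surgery, or use of an alternative robotic-assisted system". The protocol synopsis names procedure success and conversion as separate items at that visit, but procedure success is never defined or used in the derivation.

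**The concern.** A case opened with Hugo and then abandoned, or closed with the hernia unrepaired, has not been switched to anything. It is not a conversion under SAP 4.1.1, it has an answered outcome, and it belongs to the FAS. The derivation therefore makes it a success. Such a case is evidence against the claim that the system is effective for hernia repair, yet it counts in favour of that claim.

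The route matters because this is the only confirmatory effectiveness test, in a single-arm trial with site-reported outcomes. Under protocol 13.1 the Clinical Events Committee adjudicates serious adverse events, deaths and surgical site events; it does not review conversions or non-completions. The sensitivity analyses in SAP 7.9.1.7.1 deal with missing outcomes and major deviations, and none rescores an incomplete repair. There is also a smaller route to misclassification: a true switch recorded by the site under a reason other than Converted would not be picked up.

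**Working it through.** **Step 1. How each answered outcome is scored**

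| What happened after incision | Scored under SAP 7.9.1.2 |
|---|---|
| Repair completed with Hugo | Success |
| Finished laparoscopically, open or with another robot; No, Converted | Failure |
| Such a switch, but recorded under another No reason | Success, contrary to SAP 4.1.1 |
| Aborted or incomplete, no switch | Success |
| Outcome blank | Missing; handled by SAP 7.4 |

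Rows three and four are the gap.

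**Step 2. Reproduce the plan's figure**

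Inputs from SAP section 6 and protocol 14.4.1: goal 85%, expected success 93%, one-sided alpha 0.025, exact binomial test, n = 172, 10% attrition. The pass boundary is the smallest r with P(X ≥ r | n, 0.85) < 0.025.

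- n = 172: r = 156, so at most 16 failures. Actual alpha is 0.0189 and P(X ≥ 156 | 172, 0.93) = 0.904. The stated 90% is confirmed.
- 172 / 0.9 = 191.1, rounded up to 192. Confirmed.

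**Step 3. Boundary at the planned 192**

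p = P(X ≥ 192 − f | 192, 0.85) for f failures:

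| Failures | Success rate | p | Result |
|---|---|---|---|
| 17 | 91.1% | 0.0080 | pass |
| 18 | 90.6% | 0.0147 | pass |
| 19 | 90.1% | 0.0255 | fail |
| 20 | 89.6% | 0.042 | fail |

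**Step 4. Aborted cases needed to reverse a pass (n = 192)**

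The number needed is 19 minus the number of conversions.

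- 17 conversions: 19 − 17 = 2.
- Planned rate, 7% × 192 = 13.4, about 13 conversions: 19 − 13 = 6.
- Literature mean, 1.5% × 192 = 2.9, about 3 conversions: 19 − 3 = 16.

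At n = 172 and the planned rate (7% × 172, about 12 conversions), 5 are needed: 160/172 passes, and 155/172 is one short of 156.

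**Step 5. Effect over a range of abort rates (n = 192)**

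The documents give no abort rate, so the share a of FAS subjects aborted without a switch is an assumption. Column two takes 93% free of conversion and scores aborted cases as failures: P(X ≥ 174 | 0.93 − a). Column three takes 85% truly completed without conversion and applies the SAP scoring: P(X ≥ 174 | 0.85 + a).

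| a | Power, aborted = failure | Chance of passing under SAP scoring |
|---|---|---|
| 0 | 0.919 | 0.0147 |
| 1% | 0.802 | 0.0356 |
| 2% | 0.633 | 0.0785 |
| 3% | 0.446 | 0.1563 |

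**The case against.** The strongest reply is that the SAP does what the protocol says. Both define success as freedom from conversion, and the 85% goal was built from the same quantity: protocol 6.2.2 obtains the success rate by subtracting the literature conversion rate from 100%. Adding aborted cases to the failures while keeping 85% would set a broader failure definition against a goal derived for a narrower one. It would also count stops unrelated to the device, such as an eligibility problem found after incision. This stands. It bears on which remedy to choose, and it means the SAP is not in conflict with the protocol; it does not justify leaving the class without a rule.

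A second reply is that the reversal at two aborted cases needs 17 conversions, well above the planned 13. This also stands, and it limits the size of the point. Device deficiencies, adverse events and procedure characteristics are summarised as well, so aborted cases would not be wholly hidden, although none of those summaries rescores the endpoint.

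Three stronger readings are tempting and are not supported.

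- A reader might infer that every case not completed with Hugo is scored as a success. Cases finished by another method are conversions by definition.
- A reader might infer that a site could answer Yes because conversion was its planned fallback, and so bypass the conversion item. The case report form is not in the documents, and nothing in them suggests sites would answer that way.
- A reader might take the last column of Step 5 as an inflated type I error. Under the stated hypothesis, where P is freedom from conversion, values above 85% lie in the alternative and rejection is correct. Those figures are error rates only if success is redefined as completed repair.

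**Conclusion.** The point holds in a limited form. An answered case that was stopped or left incomplete after incision, with no switch of method, counts as a surgical success in the confirmatory test, and no planned analysis scores it otherwise. The gap is in protocol 5.2.1 and SAP 7.9.1.2 alike. The sample size calculation is sound.

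The consequence depends on an abort rate that the documents do not supply. With 192 subjects, two aborted cases decide the result at 17 conversions, six at the planned rate and 16 at the literature mean. It is therefore worth correcting before the data are seen, but it changes the conclusion only if aborted cases occur and the result lies within their number of the boundary.

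**What to change.** Before the database snapshot, amend SAP 7.9.1.2 as follows.

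1. State that a post-incision case in which the repair was not completed with Hugo is not a surgical success.
2. Classify every answer of No without Converted against the definition in SAP 4.1.1, so that a switch recorded under another reason counts as a conversion. Check these cases against the conversion data listed in protocol Table 7.
3. Report the number of aborted or incomplete cases, with reasons.
4. Choose one of two routes. **(a)** Score these cases as failures in the primary analysis, noting that the 85% goal was derived from conversion rates only and that the comparison is therefore conservative. **(b)** Keep the conversion endpoint for the primary test, pre-specify a sensitivity analysis scoring these cases as failures, and state the effectiveness conclusion in light of it.

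In the same edit, reconcile the wording in SAP 7.9.1 that ties conversion to failure of the Hugo system. It is a separate matter, but it would narrow the failures further.

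**Cost.** Route (b) keeps endpoint and goal aligned and needs SAP wording only. Route (a) changes the primary definition, so it needs a protocol amendment with FDA and IRB approval under protocol 16.6. It also lowers power if aborts occur: at n = 192 and 93% free of conversion, from 0.92 to 0.80 at an assumed 1% aborted and 0.63 at 2%. The observed success rate under route (a) may be slightly lower.

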7.9.1.3 Performance Requirements

The null hypothesis will be rejected if the p-value for the one-sided hypothesis test is less than 0.025.

7.9.1.4 Rationale for Performance Criteria

To determine performance criteria, analyses were performed on available literature. Point estimates along with 95% and 99% predicted intervals were calculated to provide plausible ranges of potential effect sizes. Clinically meaningful margins and statistical precisions have been taken into account to determine the appropriate performance goals. The performance goal (PG) of 85% is derived on literature research (**Table 1**).

Table 1: Primary Effectiveness Endpoint – Performance Goal Determination

Primary Effectiveness Endpoint: Surgical Success Rate		
Surgery Type	Performance goal (PG)	Rationale
Inguinal and Ventral Hernia Repair	85%	The literature-based mean effect size for conversions is 1.5% with a 95% CI of 0.2% to 9.4%. The 95% prediction interval is 0.1% to 29.3%. A PG of 85% for the surgical success rate, equivalent to a 15% conversion rate, is set, which is aligned with the upper 95% CI with an added 5.6% margin and falls within the 95% prediction interval.

7.9.1.5 Analysis Methods

The surgical success rate will be calculated as the proportion of subjects with a successful surgery. The hypothesis will be tested using the binomial test at one-sided alpha of 0.025. In the case of multiple imputation, the objective will be tested using a Z-test. The 95% two-sided confidence interval will also be reported; The confidence interval will be calculated using the Clopper-Pearson exact binomial method, with Wald confidence interval provided in the case of imputation.

7.9.1.6 Determination of Subjects/Data for Analysis

The analysis set for the primary effectiveness will be the full analysis set (FAS) for the combined inguinal and ventral hernia cohort. If 5% of the data or fewer are missing for the primary analysis, no imputation will be used. Otherwise, missing data will be imputed for the FAS using multiple imputation.

7.9.1.7 Supporting Analyses

7.9.1.7.1 Sensitivity Analysis

In the case of no imputation for the primary objective, the first sensitivity analysis will use multiple imputation (MI) to impute missing outcome data (see MI details in section 7.4). In the case of imputation, the first sensitivity analysis will use those subjects with data for the assessment.

Another sensitivity analysis will be to assess the primary objective using the PPAS, excluding subjects with major protocol deviations.

The final sensitivity analysis will be a tipping point analysis (based on the FAS) with the missing outcome data. In this analysis, missing primary outcome data will be imputed as failure to determine the proportion of subjects with missing data that would need to be converted to another form of surgery (e.g., open, laparoscopic, alternative RAS) to change the primary effectiveness endpoint conclusions.

A summary of subjects with missing data, along with reasons for missing data, will be provided.

7.9.1.7.2 Sub-group Analyses

Subgroup analysis for the primary effectiveness objective will be performed by cohort (inguinal, ventral), gender, age group (based on median age), race, and ethnicity. Sub-group analysis will be performed using FAS with available data. No imputation will be applied. Any subgroup with less than 10 subjects may not be reported.

7.9.2 Primary Safety Objectives

The primary safety objective of this study is to demonstrate that the Medtronic Hugo™ RAS system is safe when used in inguinal and ventral hernia repair. The primary objective on safety is to demonstrate that the surgical site event rate is less than the pre-defined performance goal (PG). The primary safety endpoint is the rate of subjects with one or more procedure- and/or device-related SSEs from the first incision through 30 days post-procedure.

7.9.2.1 Hypothesis

The primary safety hypothesis is to test the overall 30-day procedure- and/or device-related SSEs rate (i.e., rate of subjects with one or more procedure- and/or device-related SSEs) against a performance goal for each hernia cohort. A performance goal of 30% is pre-defined to evaluate the SSE rate. Let R be the 30-day procedure- and/or device-related SSEs rate for each specific hernia cohort. The statistical hypothesis is formulated as follows for each hernia cohort:

$$H_0: R \geq 30\% \quad \text{vs.} \quad H_a: R < 30\%$$

7.9.2.2 Endpoint Definition and Derivation

The rate of SSE within 30 days is calculated as the proportion of subjects who experience an SSE during the procedure and through 30 days after the procedure. SSE are defined in detail in section 4.1.2. The AE start date of the adverse event will be used to determine when an SSE was experienced.

7.9.2.3 Performance Requirements

Each null hypothesis will be rejected if the p-value for the one-sided hypothesis test is less than the multiplicity-adjusted alpha as described in Section 7.5 (Holm's method, i.e. Holm-Bonferroni method).

7.9.2.4 Rationale for Performance Criteria

A literature search was performed for each of the surgery types (inguinal hernia repair and ventral hernia repair) including RAS and laparoscopic procedure types. Point estimates along with 95% confidence intervals (CIs) and prediction intervals were calculated based on the reported literature data. Clinically meaningful margins and statistical precisions have been considered to determine the appropriate performance goals. The performance goals (PG) of 30% are derived on literature research (Table 2).

Table 2: Primary Safety Endpoint – Performance Goal Determination

Primary Safety Endpoint: Rate of Subjects with One or More Procedure-/Device-Related Surgical Site Events (SSEs) through 30 Days Post-Procedure		
Surgery Type	Performance Goal (PG)	Rationale
Inguinal Hernia	30%	The literature-based maximum possible SSE rate is 3.8% with a 95% CI of 2.1% to 6.9%. The 95% prediction interval is 0.3% to 36.0%. A PG of 30% falls within the 95% literature-based prediction interval and is clinically relevant.
Ventral Hernia	30%	The literature-based maximum possible SSE rate is 4.5% with a 95% CI of 1.8% to 10.8%. The 95% prediction interval is 0.3% to 45.5%. A PG of 30% falls within the 95% literature-based prediction interval and is clinically relevant. Additionally, Medtronic-sponsored clinical study data show a 14.5% procedure- and/or device-related SSI + SSO pooled rate, with a 95% CI of 8.8% to 22.0%. With an approximate 8% clinical margin added to the upper 95% confidence bound, these data support the PG of 30%.

7.9.2.5 Analysis Methods

The proportion of subjects experiencing SSE in each hernia cohort will be reported and compared against the performance goals using the binomial test. The proportion of subjects experiencing the component of SSE, i.e. SSO and SSI, will also be reported. The 95% two-sided confidence interval will be reported using the Clopper-Pearson exact binomial method.

7.9.2.6 Determination of Subjects/Data for Analysis

The analysis set for the primary safety objective will be FAS with available data at 30 days, i.e., those subjects whose status (event, no event) at 30 days can be determined. Data availability for assessments through 30 days will follow the logic described in section 7.4. The inguinal hernia cohort and ventral hernia cohort will be analysed separately.

7.9.3 Secondary Objectives

The secondary objectives of this study are to demonstrate the Medtronic Hugo™ RAS system performs as intended when used in inguinal and ventral hernia repair. The secondary endpoints of this study will assess the overall performance of the Medtronic Hugo™ RAS system when used for the robotic surgery.

The role of the secondary endpoints is to explore additional effects and outcomes associated with either the procedure or the disease state. The pre-specified performance goals serve as benchmarks for interpretation rather than thresholds for statistical significance of clinical trial success in this study.

Statistical evaluations for secondary objectives with performance goals are not powered in this study. Therefore, the secondary endpoints are planned to be analyzed descriptively with no plans for statistical

testing. Secondary objectives will be analyzed using all subjects from whom data is available. Data availability for assessments through 30 days will follow the logic described in section 7.4.

7.9.3.1 Objectives, Endpoint Definitions and Derivations

Endpoint	Endpoint Definition and Derivation
Any complication rate through 30 days post procedure	Overall rate of subjects with one or more procedure- and/or device-related complications (Clavien-Dindo Grade I or higher), from the first incision through 30 days post-procedure. CD Grade and device and/or procedure relatedness is assessed by the study site. Where CEC assessment of device and/or procedure relatedness is available, it will be used as the primary source of relatedness.
Major complication rate through 30 days post procedure	Overall rate of subjects with one or more major procedure- and/or device-related complications (Clavien-Dindo Grade III or higher), from the first incision through 30-days post-procedure. CD Grade and device and/or procedure relatedness is assessed by the study site. Where CEC assessment of device and/or procedure relatedness is available, it will be used as the primary source of relatedness.
Operative time	Time from skin incision to skin closure. This will also be summarized separately for the following: 
 • Unilateral operative time for inguinal hernia • Bilateral operative time for inguinal hernia • Operative time for ventral hernia
Readmission rate through 30 days post procedure	Admission for a direct consequence or complication associated with the treated hernia or with the surgical procedure to treat the hernia. A readmission is determined by the study site on the AE CRF.
Reoperation rate through 30 days post procedure	Operation for a direct consequence or complication associated with the treated hernia or with the surgical procedure to treat the hernia. A reoperation is determined by the study site on the AE CRF.
Recurrence rate through 30 days post procedure	Clinical hernia recurrence is defined as a palpable fascial defect and/or a clinically manifested bulge within 7 cm of the original repair, exacerbated by a Valsalva maneuver during physical examination by a study investigator. A recurrence is determined by the study site on the AE CRF. Only confirmed recurrence will be included in this rate. Secondary hernias will be differentiated from primary hernia recurrences by the study investigator. Secondary hernias are defined as a hernia located >7 cm of the original hernia repair. Secondary hernias will be excluded from hernia recurrence reporting for all hernia recurrence endpoints.
Recurrence rate through 2 years post procedure	This analysis uses similar definitions as recurrence rate through 30 days. Note: Suspected hernia recurrence(s) reported by a subject, but not confirmed by an investigator, will not be considered as a clinical hernia recurrence for this endpoint, but will be reported separately as a subject-reported recurrence in the final report.

